4. SUBJECT POPULATION

It is estimated that approximately 1,500 subjects will be randomly assigned to treatment in this study as described in Section 3.1.1, Part 1: Single-Ascending Dose and Section 3.1.2, Part 2: Dose-Response Evaluation. Subjects who are withdrawn early from the study will not be replaced. For a discussion of the statistical considerations of subject selection, refer to Section 11.2, Sample Size Determination.

The inclusion and exclusion criteria for enrolling subjects in this study are described in the following 2 subsections. If there is a question about the inclusion or exclusion criteria below, the investigator must consult with the appropriate sponsor representative and resolve any issues before enrolling a subject in the study. Waivers are not allowed.

Screening for eligible subjects in Parts 1 and 2 may be done up to 30 days before randomization, pre- or postoperatively. Subjects will be eligible for rescreening only in those cases when TKR surgery is rescheduled outside of the 30-day window. Subjects may only be rescreened on 1 occasion.

4.1. Inclusion Criteria

Each potential subject must satisfy all of the following criteria to be enrolled in the study:

- 1. Male or female of non-childbearing potential
- 2. At least 50 years of age or older
- 3. Weight \geq 40 kg to \leq 150 kg
- 4. Medically appropriate for postoperative anticoagulant prophylaxis as determined by the investigator on the basis of the physical examination, medical history, and vital signs measurements performed as part of screening for elective TKR surgery and any examinations performed as part of standard postoperative care following surgery

- 5. Medically appropriate for postoperative anticoagulant prophylaxis on the basis of clinical laboratory tests performed as part of screening for elective TKR surgery and any examinations performed as part of standard postoperative care following surgery. If the results of the laboratory tests are outside the normal reference ranges, the subject may be included only if the investigator judges the abnormalities or deviations from normal to be not clinically significant or to be appropriate and reasonable for the population under study. This determination must be recorded in the subject's source documents.
- 6. Has undergone an elective primary unilateral TKR
- 7. Must sign an informed consent form (ICF) indicating that he or she understands the purpose of, and procedures required for, the study and is willing to participate in the study.
- 8. Before randomization, a woman must not be of childbearing potential defined as:
 - Postmenopausal

A postmenopausal state is defined as no menses for 12 months without an alternative medical cause. A high follicle stimulating hormone (FSH) level (>40 IU/L or mIU/mL) in the postmenopausal range may be used to confirm a postmenopausal state in women not using hormonal contraception or hormonal replacement therapy, however in the absence of 12 months of amenorrhea, a single FSH measurement is insufficient.

• Permanently sterile Permanent sterilization methods include hysterectomy, bilateral salpingectomy, bilateral tubal occlusion/ligation procedures, and bilateral oophorectomy.

If reproductive status is questionable, additional evaluation should be considered in consultation with the sponsor.

- 9. A woman must agree not to donate eggs (ova, oocytes) for the purposes of assisted reproduction during the study
- 10. Contraceptive use by men should be consistent with local regulations regarding the use of contraceptive methods for subject participating in clinical studies.

During the study from Day 1 through the Week 18 visit, a man

- Who is sexually active with a woman of childbearing potential must agree to use a barrier method of contraception (eg, condom with spermicidal foam/gel/film/cream/suppository)
- Who is sexually active with a woman who is pregnant must use a condom
- Must agree not to donate sperm
- Must agree not to father a child

11. Willing and able to adhere to the prohibitions and restrictions specified in this protocol.

4.2. Exclusion Criteria

Any potential subject who meets any of the following criteria will be excluded from participating in the study:

- 1. Any condition for which the use of apixaban is not recommended in the opinion of the investigator (eg, spinal anesthesia procedure with bleeding or significant trauma, postoperative epidural analgesia with an epidural catheter within 5 hours of oral or IV study drug administration, previous allergic reaction, creatinine clearance <15 mL/minute or on dialysis)
- 2. Bilateral, revision or unicompartmental procedure
- 3. Known or suspected hypersensitivity or intolerance to any biologic medication or known allergies or clinically significant reactions to murine, chimeric, or human proteins, monoclonal antibodies or antibody fragments, or any of the excipients of JNJ-64179375 (refer to Investigator's Brochure)¹⁷
- 4. Unable to undergo venography (eg, due to contrast agent allergy, poor venous access, or impaired renal function that would increase the risk of contrast-induced nephropathy)
- 5. Known previous DVT in either lower extremity
- 6. Chronic anticoagulation therapy for any condition (eg, atrial fibrillation, mechanical heart valve) is required
- 7. Any preplanned invasive procedure (eg, surgery, colonoscopy) up to Week 18 for which anticoagulant or antiplatelet therapy would be interrupted
- 8. Planned use of intermittent pneumatic compression after randomization
- 9. Received an investigational drug (including investigational vaccines, experimental antibody or biologic therapy) within the previous 6 months or 5 half-lives, whichever is longer, or received any other experimental therapy, or used an invasive investigational medical device within 60 days before the planned first dose of study drug or is currently enrolled in an investigational study
- 10. Previous randomized subject in this study or participated in previous studies with JNJ-64179375

- 11. Any condition for which, in the opinion of the investigator, participation would not be in the best interest of the subject (eg, compromise the well-being) or that could prevent, limit, or confound the protocol-specified assessments
- 12. Employee of the investigator or study site, with direct involvement in the proposed study or other studies under the direction of that investigator or study site, as well as family members of the employees or the investigator
- 13. At the time of informed consent, the subject does not agree to following up with scheduled study visits or allowing a telephone contact to the subject's alternative means of contact (eg, subject's children, spouse, significant other, caretaker, legal representative, or healthcare professional), as necessary, until the end of the study, should he or she discontinue prematurely

NOTE: Investigators should ensure that all study enrollment criteria have been met at screening. If a subject's clinical status changes (including any available laboratory results or receipt of additional medical records) after screening but before the first dose of study drug is given such that he or she no longer meets all eligibility criteria, then the subject should be excluded from participation in the study. Section 9.1.2, Screening Phase, describes options for retesting. Section 17.4, Source Documentation, describes the required documentation to support meeting the enrollment criteria.

4.3. **Prohibitions and Restrictions**

Potential subjects must be willing and able to adhere to the following prohibitions and restrictions during the course of the study to be eligible for participation. Additionally, for apixaban, investigators should follow the prohibitions and restrictions in the Summary of Product Characteristics.

- 1. Refer to Section 8, Prestudy and Concomitant Therapy for details regarding prohibited and restricted therapy during the study.
- 2. Agree to follow all requirements that must be met during the study as noted in the Section 4.1, Inclusion Criteria and Section 4.2, Exclusion Criteria.
- 3. A man who is sexually active must agree to use a barrier method of contraception method as described in Section 4.1, Inclusion Criteria. All men must also not donate sperm through the Week 18 visit.
- 4. Subjects who are given permission by the treating physician to resume normal activity following TKR surgery should avoid activities that could produce significant trauma, and when participating in low-risk sports (eg, biking), proper safety gear (eg, helmet, gloves) should be worn through the Week 18 visit. In addition, subjects should be more cautious when using sharp objects (eg, razors, scissors, and knives) through the Week 18 visit.

5. Subjects should not donate blood or blood products for the duration of the study and for at least 4 weeks after the Week 18 visit.

5. TREATMENT ALLOCATION AND BLINDING

Treatment Allocation

Procedures for Randomization and Stratification

Central randomization will be implemented in this study. In Part 1, within each of the up to 6 planned cohorts, subjects will be randomly assigned to 1 of 2 treatment groups based on a computer-generated randomization schedule prepared by or under the supervision of the sponsor. The randomization will be balanced by using randomly permuted blocks and in Part 2 will also be stratified by region. The interactive web response system (IWRS) will assign a unique treatment code, which will dictate the treatment assignment for the subject. The requestor must use his or her own user identification and personal identification number when contacting the IWRS, and will then give the relevant subject details to uniquely identify the subject.

In Part 2, subjects will be randomly assigned to 1 of the treatment groups based on a computer-generated randomization schedule as previously described for Part 1. Separate randomization schedules will be used for Part 1 and Part 2 of the study.

Blinding

The investigator will not be provided with randomization codes. The codes will be maintained within the IWRS, which has the functionality to allow the investigator to break the blind for an individual subject.

Data that may potentially unblind the treatment assignment (ie, coagulation testing, study drug concentrations, antibodies to JNJ-64179375, study drug preparation/accountability data, treatment allocation, and biomarker laboratory data) will be handled with special care to ensure that the integrity of the blind is maintained and the potential for bias is minimized. This can include making special provisions, such as segregating the data in question from view by the investigators, clinical team, or others as appropriate until the time of database lock and unblinding. To maintain the blind of the study, the investigator should not measure coagulation assays locally unless considered necessary for subject clinical care. In addition, the investigator will not receive the results of the PD parameters from the central specialty laboratory during the conduct of the study.

Under normal circumstances, the blind should not be broken until all subjects have completed the study and the database is finalized. Otherwise, the blind should be broken only if specific emergency treatment/course of action would be dictated by knowing the treatment status of the subject. In such cases, the investigator may in an emergency determine the identity of the treatment by contacting the IWRS. While the responsibility to break the blind in emergency situations resides solely with the investigator, it is recommended that the investigator contact the sponsor or its designee if possible to discuss the particular situation, before breaking the blind. Telephone contact with the sponsor or its designee will be available 24 hours per day, 7 days per week. In the event the blind is broken, the sponsor must be informed as soon as possible. The date and time for the unblinding must be documented by the IWRS and the reason for the unblinding must be documented in the source document. The documentation received from the IWRS indicating the code break must be retained with the subject's source documents in a secure manner.

Subjects who have had their treatment assignment unblinded may continue on study drug unless the subject meets a study drug discontinuation criterion. Investigators should not disclose the treatment assignment to the subject whenever possible, even in a special situation where the treatment assignment has been unblinded to the investigator. Subjects who have had their treatment assignment unblinded should continue to return for scheduled evaluations.

In general, randomization codes will be disclosed fully only if the study is completed and the clinical database is closed. However, the randomization codes and the translation of randomization codes into treatment and control groups will be disclosed to those authorized individuals of the OC for the ongoing data reviews in Part 1 and of the IDMC for data reviews and interim analyses in Part 2. Refer to Section 11.10, Interim Analysis, Section 11.11.1, Operations Committee, and Section 11.11.2, Independent Data Monitoring Committee for additional details.

JNJ-64179375 (Parts 1 and 2)

Using the randomization code, an unblinded pharmacist or other appropriately licensed and authorized health professional at each study site will prepare an individual study drug dose of JNJ-64179375 or JNJ-64179375 placebo (0.9% normal saline) for each subject in a 50-mL normal saline IV bag as per the directions in the Investigational Product Preparation Instructions (IPPI). Subjects randomized to apixaban will receive a 0.9% normal saline IV bag with no active study drug. All study drugs will have a blinded label applied prior to dispensing.

Apixaban (Parts 1 and 2)

Using the randomization code, the pharmacist or other appropriately licensed and authorized health professional will dispense a bottle of blinded oral study drug (over-encapsulated apixaban tablets or matching apixaban placebo capsules) to each subject at the time of randomization. The subject will be administered the capsules from the bottle while hospitalized and will be given the bottle for outpatient use at the time of discharge from the hospital. Refer to Section 6, Dosage and Administration for additional details regarding subject dosing.

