evaluable and the true underlying total VTE event rates are 15%, 10%, 8%, and 6% at potential doses of JNJ-64179375 of 0.3, 0.6, 0.9, and 1.2 mg/kg, respectively, with a total sample size of 1,200 subjects, the study is expected to have over 90% power to declare proof-of-efficacy, which is defined as either a statistically significant dose-response trend or a total VTE event rate lower than 30% in the pooled doses of JNJ-64179375 at a 1-sided, 2.5% α -level. The exact power will vary because of the nature of the adaptive study design.

For comparison with apixaban in Part 2, if the true underlying total VTE and any bleeding event rates are as specified in Table 7, a simulation study demonstrates that there will be approximately 90% probability to identify a dose within the dose range of 0.3 to 1.2 mg/kg, of which both the model-predicted total VTE and any bleeding event rates met the prespecified noninferiority (NI) criterion (the upper bound of the 1-sided 90% CI for the odds ratio [JNJ-64179375 to apixaban] is equal to or lower than 1.5 for total VTE and any bleeding events).

Table 7:Assumed Efficacy and Safety Event Rates by Treatment Group in Sample Size Determination
for Part 2

	JNJ-64179375				Apixaban
	0.3 mg/kg	0.6 mg/kg	0.9 mg/kg	1.2 mg/kg	2.5 mg bid
Total VTE					
(Efficacy)	15%	10%	8%	6%	15%
Any Bleeding					
(Safety)	5%	6%	7%	8%	8%

bid=twice daily; VTE=venous thromboembolism

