11.3. Efficacy and Bleeding Analyses

A dose-response trend will be assessed with respect to the primary efficacy (total VTE) and safety (any bleeding) endpoints in Part 2. Depending on the number of doses studied, a set of up to 7 candidate models (doses are in logarithm scale) will be used to cover a suitable range of possible efficacy dose-response shapes (linear, Emax, exponential, sigEmax1, sigEmax2, sigEmax3, and sigEmax4) (see Figure 3).

Figure 3: Candidate Models for Total VTE (Efficacy)

VTE=venous thromboembolism

Similarly, a set of up to 6 candidate models will be used to cover a suitable range of safety doseresponse shapes (linear, Emax, exponential, sigEmax1, sigEmax2, and sigEmax3) (see Figure 4). The set of safety candidate models used will be similarly chosen as for the efficacy candidate models, which is dependent on the number of doses studied in Part 2.

Figure 4: Candidate Models for Any Bleeding (Safety)

Each of the dose-response shapes in the candidate set will be tested using the corresponding contrast *t*-test statistic, employing a critical value derived for the maximum of the *t*-test statistics (based on the associated multivariate *t*-distribution) to ensure appropriate multiplicity correction that preserves the Type I error rate. A dose-response trend is established for an endpoint when the maximum of the *t*-test statistics for the corresponding endpoint exceeds the critical value.

Predicted event rates at a specific dose will be derived for each candidate model. The weighted average of these predicted event rates (weights are determined by the model goodness-of-fit), will then be used to estimate the target dose.^{4,16} The minimum dose that meets the NI efficacy criterion (defined as the upper bound of the 1-sided 90% CI for model-predicted JNJ-64179375/apixaban odds ratio less than 1.5) is considered as the minimum effective dose. The highest dose to be considered to proceed is the maximum dose that meets the NI safety criterion (defined as the upper bound of the 1-sided 90% CI for model-predicted JNJ-64179375/apixaban odds ratio less than 1.5). Any dose between the minimum effective dose and the highest dose to proceed is considered an eligible dose to be further studied in a subsequent study(ies). The final dose selection will be based on the consideration of the total benefit-risk balance.

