The determination of the NI criterion above is based on 2 considerations: 1) distribution of the point estimate for the odds ratio for the given sample size when the NI criterion is met; and 2) the balance between the false-positive rate (incorrectly conclude an inferior dose to be comparable to apixaban) and the false-negative rate (incorrectly conclude an efficacious dose to be inferior to apixaban). With the given sample size and event rates as specified in Table 7, the

median corresponding odds ratio in 10,000 simulated studies is approximately 1.0 for total VTE and 0.94 for any bleeding. With the same assumptions, these NI criteria will yield approximately 90% probability to correctly identify an eligible dose for subsequent study(ies).

The details of the adaptive decision guidelines for adding and/or dropping treatment groups or changing the randomization ratio in Part 2 will be specified in the IDMC charter and the Part 2 SAP.

Prespecified clinical variables of interest for the efficacy subgroup analyses include region, age, sex, weight/body mass index, renal function, surgery duration, TXA use, tourniquet use, and mechanical VTE prophylaxis device use. The same variables will be used for safety subgroup analyses with the addition of aspirin/NSAID use.

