1. INTRODUCTION

This Part 1 Statistical Analysis Plan (Part 1- SAP) specifies definitions of analysis sets, key derived variables, and statistical methods for analysis of safety and efficacy for the Dose Escalation (Part 1) part of the Phase 2 study. This SAP is based on the Clinical Protocol JNJ-64179375THR2001 amendment dated September 11, 2017. Titles, mock-ups and programming instructions for all statistical outputs (tables, figures, and listings) will be provided in a separate document entitled Data Presentation Specifications (DPS). A separate Part 2 SAP will address the analyses pertaining to Part 2 of the study.

Part 1- SAP and its associated DPS will be used to generate a Topline report at the end of Part 1 of the study.

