b) For the unblinded data review planned after all subjects are expected to have completed the Day 10-14 visit for Part 1, the following summary and analysis will be performed.

- Incidence of total VTE, major VTE with associated component events up to day 10-14 visit observation period will be summarized by treatment group for the modified ITT (mITT) analysis set. 90% confidence intervals for the odd ratio of each JNJ-64179375

dose over apixaban event rate with respect to Total VTE and Major VTE events will also be constructed.

- Dose response of JNJ-64179375 with respect to total VTE will be assessed using a two-stage generalized least squares approach model fitting methodology (Pinheiro et al, Stat in Med, 2013). That is, in the first stage, ANOVA-type model to the binary, total VTE data, based on the logistic regression model are fit using dose as factor. In the second stage, various candidate models (on logit scale) are fit using the estimates (from first stage) employing the Multiple Comparisons and Modeling (MCPMod) approach to the dose levels and associated variance-covariance matrix estimates from stage 1. The following candidate models will be considered: linear, emax, exponential, logistic and sigEmax. Dose-response effect are tested using a model-based multiple contrast test to select one (or several) model(s) from the significant shapes. The best fitting model to the data are picked using either the gAIC or aveAIC model selection criterion. The model with the smallest gAIC or aveAIC value is considered to fit the data best. Plots of the observed data and model fit including the 95% confidence intervals of the fitted lines will be presented using response rate on the y-axis and dose on the x-axis

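### Part 2 randomization is stratified by region, but the stated dose-response analysis has no region term; with adaptive allocation and a drifting regional mix the trend test can miss its 2.5% level

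*Protocol*

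**What the plan says.** Protocol section 5 makes region the one named stratification factor in Part 2: "The randomization will be balanced by using randomly permuted blocks and in Part 2 will also be stratified by region".

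Protocol section 11.3 sets out the Part 2 analysis. It begins: "A dose-response trend will be assessed with respect to the primary efficacy (total VTE) and safety (any bleeding) endpoints in Part 2". On the test itself it says: "Each of the dose-response shapes in the candidate set will be tested using the corresponding contrast" t-statistic, with a critical value for the maximum. Model-averaged predictions then give odds ratios versus apixaban. A dose is eligible for further study when the upper 1-sided 90% bound is below 1.5 for both efficacy and bleeding. No covariate or stratum is mentioned. Region appears once in that section: "Prespecified clinical variables of interest for the efficacy subgroup analyses include region, age, sex" and other variables.

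Protocol section 11.10 keeps allocation balanced only until the first interim. After about 400 and 800 subjects, doses may be added or dropped and the ratio changed.

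The SAP supplied covers Part 1 only: "A separate Part 2 SAP will address the analyses pertaining to Part 2 of the study". Its first-stage model is "based on the logistic regression model are fit using dose as factor" (section 5.2.3), its section 2.2 keeps center out of every model, and its section 1.5 says Part 1 has no stratification. Protocol section 11 says the Part 2 SAP will be updated before the first Part 2 consent.

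**The concern.** Stratifying by a factor and then leaving it out of the model usually costs only a little efficiency. Here there is a second issue. Within each stage and region, randomization is valid. Once the allocation ratio differs between stages, pooling the stages keeps dose independent of region only if the regional mix stays the same. If the mix drifts, doses favoured late carry more late-enrolling regions, and any regional difference in VTE risk looks like a dose effect.

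Two outputs are at stake: the trend test, which carries Part 2's primary objective, and the odds ratios versus apixaban that decide which doses are eligible for later study.

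**Working it through.** **Inputs from the documents.** Part 2 has 1,200 subjects, up to four doses plus apixaban, 80% evaluable venography and a 1-sided 2.5% level. For the rates, protocol section 11.2 says: "evaluable and the true underlying total VTE event rates are 15%, 10%, 8%, and 6% at potential doses" of 0.3, 0.6, 0.9 and 1.2 mg/kg.

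**Assumed inputs (not in the documents).** These are two regions with total VTE of 9% and 15%, the drift in regional mix, and the adapted ratios. The two rates are the apixaban results of the two trials in protocol Table 5 (104/1157 and 147/976), used only as a scale. Their odds ratio is (0.15/0.85)/(0.09/0.91) = 1.78, about 1.8.

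**Step 1: the plan's own power.**
- Evaluable on active doses: 1,200 × 4/5 × 0.80 = 768, or 192 per dose.
- Pooled rate: (15 + 10 + 8 + 6)/4 = 9.75%.
- An exact binomial test against 30% rejects at 205 or fewer events (205/768 = 26.7%), so power is about 100%. The stated figure of over 90% reproduces by this route alone.
- The trend route alone gives about 84% (simulated MCP-Mod with assumed shapes, because the figure of candidate models is not available) to 87% (single log-dose contrast).

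**Step 2: power lost by omitting region.** With balanced arms and a regional odds ratio of 1.8, logistic trend power is 86.7% unadjusted and 86.9% adjusted. Separate simulations give 87.2% against 87.4%, and 86.1% against 86.3%. The loss is about 0.2 points each time. Even at an odds ratio of 5 it stays below 2 points.

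**Step 3: how confounding arises.** Take dose shares of (20, 20, 20, 20)%, (10, 20, 20, 30)% and (0, 20, 25, 35)% in the three stages, the remaining 20% on apixaban, and a high-risk share of 80/50/20%. VTE is flat across doses within each region. The high-risk share on each dose, and its expected rate (9% + 6% × share), are:

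| Dose | High-risk share | Expected VTE |
|---|---|---|
| Lowest | (16 + 5 + 0)/30 = 0.70 | 13.2% |
| Second | (16 + 10 + 4)/60 = 0.50 | 12.0% |
| Third | (16 + 10 + 5)/65 = 0.48 | 11.9% |
| Highest | (16 + 15 + 7)/85 = 0.45 | 11.7% |

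A downward trend appears with no dose effect.

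**Step 4: simulated one-sided error of the log-dose trend test** (nominal 2.5%; 9% and 15% regions). Strong adaptation is the allocation in step 3. Mild is 15/20/20/25% after the first interim. Ranges cover separate simulation runs.

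| Regional mix | Adaptation | Unadjusted | Region-adjusted |
|---|---|---|---|
| Constant | Strong | 2.6% | 2.7% |
| 80/50/20% | None | 2.4% | 2.5% |
| 60/50/40% | Mild | 2.7% | 2.6% |
| 60/50/40% | Strong | 3.5% | 2.6% |
| 80/50/20% | Strong | 5.6–6.4% | 2.6–2.7% |
| Opposite swing | Strong | 0.8–1.0% | 2.6–2.8% |

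An MCP-Mod version (4,000 runs, simulation standard error about 0.25 points, drift 70/50/30%) agrees:
- After a mild shift to (15, 20, 30, 35)% of active subjects, the unadjusted error is 3.5% at a regional odds ratio of 1.8 and 3.8% at 3.
- After a strong shift to (5, 5, 45, 45)%, it is 4.5% and 7.1%.
- With a region term, all four cases lie between 2.3% and 2.9%.

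**Step 5: odds ratio versus apixaban.** Assume equal apixaban allocation in each stage and the 80/50/20% swing. Apixaban pooled over stages has 0.5 × 15% + 0.5 × 9% = 12.0% VTE. A truly equal dose given only in stage 3 has 0.2 × 15% + 0.8 × 9% = 10.2%. The apparent odds ratio is (0.102/0.898)/(0.120/0.880) = 0.83, where the within-region value is 1.0.

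**The case against.** The strongest reply is that protocol section 11 is expressly a general description and leaves specifics to the SAP. Section 11.3 names no covariates at all, so its silence on region need not be a decision to analyse unadjusted. The dose-only model belongs to Part 1, which has no stratification. This stands. A reader might infer that the final Part 2 analysis will omit region, but the documents do not show that, because the Part 2 SAP is a separate document not available here.

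Three other stronger readings also fail:
- **Different regional enrolment speeds break the test.** They do not if the mix is constant over time or allocation is fixed (step 4).
- **The 9.0% and 15.0% rates show a regional difference.** They come from two separate trials with different enoxaparin comparators. Protocol section 3.2 says only that rates vary across studies.
- **Proof-of-efficacy is at risk.** It needs a trend or a pooled rate below 30%. At true rates of 9% to 15% the pooled criterion is genuinely met, whatever the trend test shows.

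It can also be said that the 6% figure stacks several assumptions. That is so, and it is an extreme case. What remains is that the adaptive rules allow the combination, the direction of error cannot be known in advance, and the remedy is already standard for a stratified design.

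**Conclusion.** The gap in the stated plan is real, and the harm is conditional. The power argument is negligible. The case for adjustment rests on error control and on unconfounded odds ratios. The trend level departs from 2.5% only when changed allocation, drifting regional mix and different regional risk occur together, and the documents quantify none of these. The departure can run in either direction. The apixaban odds ratios used for dose eligibility are exposed to the same mechanism. This is worth correcting while the Part 2 SAP can still be updated; it does not undermine the design.

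**What to change.** In protocol section 11.3 and the Part 2 SAP:
- Define the regions, and include region as a factor in the first-stage logistic model that supplies dose estimates and their covariance to MCP-Mod, for both total VTE and any bleeding.
- Use the same adjustment for the odds ratios versus apixaban.
- Prespecify a rule for combining regions with few events.
- Consider a stage term (before or after each interim), because region alone does not remove time drift from other causes.

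The cost is one or two model terms and no operational change. There are two small downsides: sparse strata must be combined, and the odds ratios become conditional on region, which the SAP should state.
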